- Aim 3.** Do women with untreated depression have a higher fetal risk than women without depression? (Cohort D vs. E).
- Aim 4.** Does the treatment effectiveness differ between women with depression only and women with depression and other comorbidity?

Exploratory analyses will be conducted to examine whether treatment effectiveness (Aims 1 & 2) is impacted by baseline depression severity. The aims will be refined with continued input from stakeholders. This will be the first large scale comparative effectiveness study to answer pressing clinical questions with an innovative and efficient two-stage design.

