Point and interval estimates of the relative hazard of PTD associated with each treatment modality (A, B, C), relative to no treatment (D) will be calculated via semiparametric maximum likelihood estimates of Cox proportional hazards regression parameters, with adjustment for potential confounders, as described above. In determining potential confounders in our regression models, we will first examine risk factors that may be plausibly linked to depression and PTD. Inclusion of potential confounding factors in our final regression models will be evaluated based on comparison of adjusted and unadjusted relative hazard ratios⁷⁹. Departures from model assumptions will be assessed via diagnostic plots of weighted residuals and tests for interaction between exposure and time (gestational age). The assessment of confounding variables for inclusion in regression models and testing of model assumptions will be performed in the stage-two sample using standard software for fitting Cox regression models. After determining the appropriate set of confounders and that there are no departures from model assumptions, the stage-one information on primary exposure and outcome will be incorporated using the semiparametric maximum likelihood estimator. This process applies to analyses of the remaining aims.

These comparisons will allow us to assess possible treatment effects on reducing PTD through both pharmacotherapy and psychotherapy. When compared to untreated (Cohort D), the comparison will be made after controlling for underlying severity of depression as measured by PHQ-9 scores or clinical diagnosis of severity before treatment. Table 2 shows that depression severity is relatively comparable among comparison groups, allowing control for confounding by indication (underlying depression severity, a unique strength of the proposed study due to the availability of PHQ-9 scores through the universal depression screening).

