We will also examine the possible dose-response in the association between antidepressant use and PTD by examining dosage of use, duration of the use, and timing of effect (single vs. multiple trimesters), in the context of time-dependent covariates. Similarly, we will also assess any dose-response relationship in the association between psychotherapy and PTD (the number of sessions received) and the effect of timing of treatment, also both as time-dependent covariates. If sample sizes allow, we will also examine the effect of combination of dose and timing (e.g., dose-response during early and late pregnancy). In addition, we will examine difference in the type of antidepressants (SSRI vs. non-SSRI).

Analyses of LBW as the outcome will parallel those described above for PTD, but logistic regression techniques will be used rather than Cox regression.

Aim 2. Head-to-head comparison of treatment regimens among Cohorts A, B & C, respectively

We will obtain point and interval estimates of relative hazards of PTD associated with the three pairwise contrasts among the three treatment groups. These estimates, and associated tests of significance, will be obtained using the Cox proportional hazards regression model developed in addressing Aim 1, fully adjusted for potential confounders including depression severity, as described above, via transformed linear contrasts of treatment group associated regression parameters. Based on the results of Aim 1 analyses of dose-response, we will obtain confounder adjusted relative hazards associated with PTD with levels of dose of a given treatment modality

(e.g. antidepressants, <30 days, 30-120 days, > 120 days duration during pregnancy), vs. particular levels of dose of another treatment (e.g. psychotherapy, ≥ 4 visits that has shown to be effective). We would categorize the comparator treatment (e.g., psychotherapy), based on the Aim 1 findings that the effectiveness of the comparator treatment in reducing risk of PTD varied by dose (e.g. no effect for < 4 visits).

As a secondary (exploratory) analysis, we will evaluate the treatment effectiveness separately for those with more severe underlying depression before treatment vs. those with more mild depression. Treating depression may be more beneficial for those with severe depression.

Analyses of LBW as the outcome will parallel those described above for PTD, but logistic regression techniques will be used rather than Cox regression.

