Aim 3. Risk of PTD & LBW for untreated depression (Cohort D vs. E)

Cox proportional hazards regression will be used to obtain point and interval estimates of the hazard ratio for PTD associated with untreated depression, vs. no depression, with adjustment for potential confounders, as described above. Parameter estimation, the approach to inclusion of potential confounders and model diagnostics are as described above for Aim 1 analyses.

To evaluate potential dose-response relationships, we will examine the strength of the association between PTD and severity of depressive symptoms. Severity will be based on results of the KPNC universal screening and clinical diagnosis of depression from the KPNC EMR. Those with a clinical diagnosis of depression will be considered to be the most severe cases followed by those who screened positive with PHQ-9 higher scores (e.g., > 20). Those who screened positive, but with lower PHQ-9 scores (10-19) will be considered to have moderate depression. The effect of severity will also be examined in terms of duration.

Analyses of LBW as the outcome will parallel those described above for PTD, but logistic regression techniques will be used rather than the Cox model.

Aim 4. Difference in treatment effectiveness by depression type (with and without comorbidity)

Analyses of Aims 1, 2 and 3, will be initially stratified by depression type, with or without other psychiatric comorbidity (yes/no). Heterogeneity in treatment effectiveness by depression type will be assessed by inclusion of appropriate cross-product (interaction) terms in regression models outlined above, using a likelihood ratio test. If there is evidence of heterogeneity, point and interval estimates of relative hazards/odds ratios of interest by comorbidity status (yes/no), adjusted for confounders, will be obtained via linear combination of regression parameter estimates (main effect and interaction terms, as appropriate).

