6.2 Avoidance of bias

The most important strength of the proposed study is the existence of the unique KPNC region-wide universal peripartum depression screening program. Such a universal screening provides a rare opportunity to conduct a large scale (N= 88,000) population-based comparative effectiveness study of depression treatment on reducing fetal risk, while avoiding potential selection bias. Without such a screening program, a large percentage of pregnant women with depression (>50%) would not have been identified, since depression during pregnancy is

substantially under-recognized and under-diagnosed^{5, 14, 45}. Thus, relying solely on clinical diagnosis of depression would likely lead to self-selection bias.

Given that randomized clinical trials are not feasible for evaluating treatment effectiveness on reducing fetal risk due to ethical concerns about assigning women into a treatment group with potential fetal risk, the proposed two-stage prospective cohort study is likely one of the best alternatives to examine the comparative effectiveness of treating depression during pregnancy. In addition to significantly reducing self-selection bias, the results of universal screening will provide information on depression severity measured by PHQ-9 score for participants. This valuable information will allow us to control for not only depression (yes/no), but also depression severity (a continuous scale) at baseline. While the distribution of depression severity was comparable among treatment groups (Table 2), ability to control for confounding by indication in such a refined detail will substantially increase the validity of our findings. Such a refined control for baseline depression severity is not likely feasible in other settings without universal peripartum depression screening.

We have also implemented several analytic methods to address the issue of possible selection into various treatment groups including *propensity score* analysis for balancing unobserved factors among treatment group and *instrument variable* analysis for possible unmeasured confounders (see Analytic Methods).

Finally, the findings from this observational study based on real world clinical experience is more relevant and applicable to actual clinical practice compared to findings from much controlled settings with selected populations (RCTs).

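### The plan asks whether baseline severity changes the treatment effect, but specifies only separate severe and mild estimates and no interaction term to compare them

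*Combined protocol and SAP*

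**What the plan says.** Section 2 (Study Objectives) announces exploratory work to "examine whether treatment effectiveness (Aims 1 & 2) is impacted by baseline depression severity". The method appears once, as a secondary exploratory analysis under Aim 2 in section 6.1: "we will evaluate the treatment effectiveness separately for those with more severe underlying depression before treatment vs. those with more mild depression". The next sentence gives the expected direction: "Treating depression may be more beneficial for those with severe depression". No cutoff between severe and mild is stated for this analysis, and there is no rule for comparing the two results.

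The plan uses the relevant tool for another modifier. Under Aim 4, "Heterogeneity in treatment effectiveness by depression type will be assessed by inclusion of appropriate cross-product (interaction) terms", with a likelihood ratio test. There the modifier is psychiatric comorbidity. The only other interaction test is under Aim 1, between exposure and gestational age, and it checks model assumptions.

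Elsewhere severity has different jobs. It is a stratification or adjustment variable against confounding by indication (sections 3.1.3 and 6.1, Aims 1 and 2) and a dose-response exposure for untreated versus non-depressed women (Aim 3). Section 6.2 counts it a strength that the study can control for "also depression severity (a continuous scale) at baseline".

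**The concern.** Whether an effect varies with severity is a question about the difference between two effects. An estimate in severe women and another in mild women each answer a different question, namely whether treatment works in that group. Each half has fewer events than the whole, so one interval will often exclude 1 while the other does not, even when the true effects are equal.

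The plan already expects more benefit in severe depression, so a one-sided pattern could easily be taken as confirmation. If the severe group is the smaller one, the more likely false pattern is the reverse: apparent benefit in mild women only. Section 8 intends findings to reach practice guidelines and patient materials, so an unsupported severity difference could travel beyond the exploratory label.

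**Working it through.** **Inputs from the documents (section 6.2.2).** Two-sided alpha 0.05 and 80% power; 400 per cohort in stage two; effective size 1,600 per cohort with the two-stage estimator; preterm delivery (PTD) rate 8% to 11%, midpoint 9.5%.

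**Assumptions.** The same HR in both severity groups; HR 0.7 or 0.6; the severe share of women is 50% or 20%; 9.5% is the untreated rate in both severity groups. The severity distribution (Table 2) is not in the text available to me.

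**Step 1: reproduce the plan's own figures.** Read the PTD rate r as the reference-group rate, so events E = (N/2) × [r + 1 − (1 − r)^HR]. Then power = Φ(√(E/4) × |ln HR| − 1.96).

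| N | r | Stated HR | E | Power |
|---|---|---|---|---|
| 800 | 8% | 1.83 | 88.6 | 81.2% |
| 800 | 11% | 1.69 | 115.5 | 80.5% |
| 3,200 | 8% | 1.38 | 301.9 | 79.9% |
| 3,200 | 11% | 1.32 | 404.1 | 79.7% |

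The stated detectable hazard ratios reproduce on this reading.

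**Step 2: an example near the design power.** With 1,600 per cohort, HR 0.7 and an untreated rate of 9.5%, the treated rate is 1 − 0.905^0.7 = 6.75%. Events are 152 and 108. Var(ln HR) = 1/152 + 1/108 = 0.0158, SE 0.126, z = 0.357/0.126 = 2.83, power 81%.

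**Step 3: split evenly by severity.** Each half has 800 per cohort, with 76 and 54 events. Variance is 1/76 + 1/54 = 0.0317, SE 0.178, z = 2.00, power 52%. The chance that exactly one half is significant is 2 × 0.52 × 0.48 = 50%.

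**Step 4: 20% severe.**
- Severe: 320 per cohort, 30.4 and 21.6 events, variance 0.0792, power 24%.
- Mild: 1,280 per cohort, 121.6 and 86.4 events, variance 0.0198, power 72%.
- Exactly one significant: 0.24 × 0.28 + 0.72 × 0.76 = 61%. About 54 of those points are the pattern of benefit in mild women only.

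**Step 5: sensitivity, even split.** The same formula gives:

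| Per cohort | HR 0.7 | HR 0.6 |
|---|---|---|
| 1,600 | 50% | 34% |
| 400 | 28% | 40% |

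With no effect in either group it is 2 × 0.05 × 0.95 = 9.5%.

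**Step 6: interaction test.** When the effects are equal, a two-sided 0.05 test calls them different 5% of the time. Simulation with 400,000 draws gave 5.0% at an even split and 5.1% at 30/70.

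**Step 7: precision of that test.** Detectable ratio of HRs = exp(2.80 × √(V_severe + V_mild)). For the even-split example, √(0.0317 + 0.0317) = 0.252 and exp(2.80 × 0.252) is about 2.0. For the 20% example, √(0.0792 + 0.0198) = 0.315 and the ratio is about 2.4. Across the plan's PTD rates, read as either the reference-group or the overall rate, an even split gives roughly 1.75 to 2.0 at effective N = 3,200 and roughly 2.8 to 4 on stage two alone.

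**The case against.** The strongest reply is that the harm depends on a reading the plan does not state. A reader might infer that a severity difference will be declared when one group is significant and the other is not. The documents do not say so. They plan point and interval estimates, and a careful reader could compare those. This stands: every discordance percentage above is conditional on that reading. What remains is that the plan asks the comparison question and gives no quantity that answers it.

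Second, the analysis is exploratory in both places where it appears, carries no power claim and feeds no numbered aim. Aim 4 also begins with stratified estimates before its cross-product test, and nothing forbids a test for severity. This limits the weight of the point. It does not make two separate estimates an answer to the question in section 2.

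Third, the severity inputs are assumed. A reader might go further and say that the severe group is too small to analyse. If severe meant a PHQ-9 above 20 and held 10% to 20% of women, 400 × 0.095 × 0.10 to 0.20 gives about 4 to 8 PTD events per cohort. But that is a stage-two-only count, the final estimator also uses stage-one data, and the cutoff is an example from Aim 3. The documents do not support the stronger claim.

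Fourth, a reader might infer that a continuous PHQ-9 interaction is a ready and much more powerful replacement. Any such advantage rests on an assumed gradient that the documents do not supply. Nor does PHQ-9 alone cover the plan's severity measure: women can enter by clinical diagnosis (section 5, Cohort D), and Aim 3 ranks diagnosed women as most severe. This stands and shapes the fix.

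**Conclusion.** The concern holds in a limited form. The plan poses an effect-modification question by baseline severity and gives only subgroup estimates as the method, while specifying the appropriate interaction test for comorbidity alone. If the two results were read by significance, equal effects would look different about 50% of the time at the plan's effective size (HR 0.7, PTD 9.5%, assumed even split) and about 61% with an assumed 20% severe share, against 5% for an interaction test. These figures rest on that reading, on a common HR and untreated rate, and on severity shares that the available text does not give. The numbered aims are unaffected. Importance: minor to moderate.

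**What to change.** In the exploratory paragraph under Aim 2 in section 6.1, add a treatment-by-baseline-severity cross-product term to the Aim 1 and Aim 2 Cox and logistic models, with a likelihood ratio test as in Aim 4. Report the ratio of hazard ratios (odds ratios for low birthweight) with its 95% CI. Present the severe and mild estimates as descriptive, with a cutoff fixed in advance, and draw no conclusion about a severity difference from them without the interaction estimate.

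Use the plan's own severity measure: continuous baseline PHQ-9 where a pre-treatment score exists, with women classified by clinical diagnosis placed in a prespecified category or covered by a sensitivity analysis.

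The cost is a short text change, one or a few model terms per contrast, and a decision on how to code diagnosed women. PHQ-9 scores and diagnoses are already in the medical record, so no new data collection is needed. The limit is precision: only a large ratio of HRs is detectable with 80% power. The plan should therefore say that the result remains exploratory and that a non-significant interaction is not evidence of equal effects.

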6.1.1 Propensity Score Analysis

In addition to the conventional analyses outlined above, we will apply a propensity score (PS) analysis method to reduce or correct for any selection bias into treatment groups in our conventional approach described above. PS analysis uses information about all measured covariates to balance unobserved factors between treatment groups. It is not necessary to know the exact relationship of unobservable factors with measured covariates - as long as there is any type of relationship between unobservable and measured factors, propensity score analysis can reduce over 90% of selection bias associated with unobserved factors⁸⁰. Given the study aims, which primarily focus on various pair-wise comparisons of treatment groups, PS analyses will be

conducted in the cohort subsets consisting of each pair of groups of interest. This will allow us to construct a multivariable logistic model for dichotomous outcomes to calculate a propensity score, i.e., the probability of receiving a given treatment, vs. another treatment (or no treatment), as a function of all known factors that might affect the treatment outcome. This model will include the same variables used in our conventional Cox proportional hazards/logistic regression models described above. The resulting probabilities (propensity scores) will be used to analyze the extent of overlap on all covariates, using graphical methods and frequency distributions. Areas of non-overlap in score between treatment groups will be trimmed (removed) from analyses. Stratified Cox proportional hazards models, with stratification on deciles of propensity score, will be used to compare the two treatment groups with respect to PTD risk^{81, 82}. Logistic regression analyses of low birthweight will include the categorized score as a covariate. We will compare results from our conventional regression models with results from the PS analysis. We note that results with adjustment for confounding via propensity score techniques are not expected to appreciably differ from results using traditional regression adjustment^{81, 83}. If we find that results differ, we will report the PS analysis results as our main findings due to the correction for selection bias in our measured characteristics.

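### Section 6.1.1 lets the propensity score result become the main finding whenever results 'differ', without defining a difference, its level or the comparator; separately, it overstates what the score does for unobserved factors

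*Combined protocol and SAP*

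**What the plan says.** The main analysis in section 6.1 is a Cox model for PTD and a logistic model for low birthweight, fitted by SMLE. It uses exposure and outcome on all 88,000 women and confounders on the 3,600 interviewed. Under Aim 1, confounders are chosen and model assumptions checked with standard Cox software in the stage-two sample, and stage-one information is then added.

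Section 6.1.1 adds PS analyses, "conducted in the cohort subsets consisting of each pair of groups of interest". On covariates: "This model will include the same variables used in our conventional Cox proportional hazards/logistic regression models described above". Non-overlapping regions of the score are trimmed, and the PTD model is stratified on score deciles. Results are "not expected to appreciably differ from results using traditional regression adjustment". The rule then follows: "If we find that results differ, we will report the PS analysis results as our main findings". The reason given is that these become "our main findings due to the correction for selection bias in our measured characteristics".

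On unobserved factors, the same section claims: "propensity score analysis can reduce over 90% of selection bias associated with unobserved factors". The only condition it attaches is a loose one, that this holds "as long as there is any type of relationship between unobservable and measured factors". Section 6.2 repeats that PS is "for balancing unobserved factors among treatment group". Section 6.1.2 (instrumental variable analysis, IVA) accepts that unmeasured confounding may remain in the PS analysis.

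**The concern.** The rule selects the headline estimator by looking at two results. Three things are missing: a metric or threshold (the nearest wording is the expectation that results will not appreciably differ), the level at which the switch operates (contrast, outcome, depression type, aim or study), and the comparator (the SMLE or the stage-two conventional fit).

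Nor is a difference by itself a reason to prefer PS. The score is built from the variables already in the regression, so the stated reason, correction for measured characteristics, applies to both analyses. Trimming changes which women are analysed, and decile stratification changes the form of adjustment. Either can move the estimate when the regression is unbiased.

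At stake is which estimator is the main finding for up to 24 treatment estimates: 6 contrasts (3 in Aim 1, 3 in Aim 2) x 2 depression types x 2 outcomes. Aim 2 takes its contrasts from a single fitted model, so switching contrast by contrast could leave a main table that mixes two estimators.

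The wording on unobserved factors is a separate matter. It invites a stronger conclusion about residual confounding than section 6.1.2 allows.

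**Working it through.** **1. Which women the PS analysis uses.** Section 3.1.3 leaves confounders absent from the medical record to the stage-two interview, and section 4.1.3 adds multivitamin intake and physical activity. A score with the same variables as the conventional models therefore needs stage-two women: 400 + 400 = 800 per pair. No two-stage PS estimator is described.

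**2. The plan's own precision figures (section 6.2.2).** With two-sided alpha 0.05 and power 0.80, solve ln(HR) x sqrt(D)/2 = 1.960 + 0.842 = 2.802. Here D = n[r + 1 - (1 - r)^HR], n is women per group and r is the reference PTD rate.

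| Women per group | r = 8% | r = 11% | Plan |
|---|---|---|---|
| 1,600 (SMLE, effective) | 1.38 | 1.32 | 1.32-1.38 |
| 400 (stage two) | 1.82 | 1.69 | 1.69-1.83 |

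The figures reproduce closely. The 1,600 is the plan's 4.0 x 400, where 4.0 is the lowest relative efficiency in its simulation (range 4 to 82).

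**3. Chance disagreement, stage-two PS against SMLE.** Assume no bias in either, a PS estimate as precise as the stage-two fit, and efficiency E = 4.
- Stage-two standard error of ln(HR): sqrt(2/(400r)) = 0.250 at 8% and 0.213 at 11%.
- SMLE standard error: half of these, 0.125 and 0.107.
- SD of the difference: stage-two standard error x sqrt(1 - 1/E) = 0.217 and 0.185.
- More than 10% apart: 2[1 - Φ(ln 1.1/0.217)] = 0.66 and 2[1 - Φ(ln 1.1/0.185)] = 0.61.
- More than 20% apart: 0.40 and 0.32.
- At E = 82, the plan's maximum, the 10% figures are 0.70 and 0.65.

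The 10% and 20% bands are assumed, since the plan gives none.

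**4. Coverage of the reported 95% interval under the rule.** Same assumptions, 2,000,000 simulated pairs per setting. At a zero band PS is always reported and coverage is 95.0%. For bands of 5% to 25% it falls from 94.1% to 91.5%.

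**5. Same-women comparison.** If both fits use the same 800 women, SD of the difference = stage-two standard error x sqrt(2(1 - ρ)).
- ρ = 0.99: 0.035 and 0.030, so 0.7% and 0.2% are more than 10% apart.
- ρ = 0.90: 0.112 and 0.095, so 39% and 32%.

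The correlations are assumed. A direct simulation (400 per group, six normal covariates, PTD 9.5%, adjusted Cox against trimmed PS-decile stratification, 600 runs at each of two confounding strengths) gave 1.0-1.3% over 10% and none over 20%.

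**6. Unobserved factors.** One measured covariate has correlation r with one unobserved factor. With 400,000 simulated women and decile stratification, the share of the unobserved factor's imbalance removed is:

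| What drives treatment | r = 0.3 | 0.5 | 0.7 | 0.9 |
|---|---|---|---|---|
| Unobserved factor only | 8% | 23% | 46% | 77% |
| Both (log-odds slopes 0.35 unobserved, 0.7 measured) | 34% | 55% | 71% | 88% |
| Measured covariate only | about 96% | about 96% | about 96% | about 96% |

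The share removed depends on what drives treatment choice as well as on the correlation. The existence of some relationship does not deliver 90%.

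**The case against.** The rule is written down in advance and runs one way, so the sponsor cannot simply pick the preferred estimator. A reader might infer free choice between two results, but the text does not support that; only the trigger is open.

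A reader might also infer that most headline results will switch. That does not follow. The 61-66% needs the SMLE as comparator, an assumed band, and an efficiency that section 6.2.2 itself calls very crude. The plan already fits Cox models in stage two, and against those the figure may be near 1%.

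A third inference would be that PS might be run on stage one without the interview confounders, so that the rule promotes the less adjusted result. The same-variables sentence rules that out.

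Nor is the larger detectable ratio a hidden loss, since section 6.2.2 presents 1.69-1.83 as its conservative basis. Nor does the rule always do harm. At PTD 9.5% with a 10% band, an SMLE biased by a factor of 1.2 covers 64% and the rule 86%. With PS biased by 1.2, the rule covers 86%, fixed PS 87.5% and fixed SMLE 95%. These runs do not show that the SMLE must be primary.

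On unobserved factors, a reader might conclude that 90% removal needs a correlation near 0.95. That holds only when the unobserved factor alone drives treatment. What the cited source says was not checked.

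All of this limits the size of the problem. It does not supply the missing definition, level or comparator, and it does not rescue the claim as worded.

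**Conclusion.** The point stands as a change the plan should make. The choice of main finding depends on an undefined comparison made after both results are known, and a difference would not show which result is less biased. How often a switch would occur runs from about 1% or less to over 60% of PTD contrasts at an assumed 10% band, largely according to a comparator the plan does not name. These percentages are illustrations. In the SMLE case without bias, the coverage loss is at most about 3.5 points (95.0% to 91.5%), and a switch returns the detectable PTD hazard ratio from 1.32-1.38 to 1.69-1.83.

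The statement on unobserved factors is too strong as written. It conflicts with the plan's own reference to measured characteristics and with section 6.1.2. PS balances unobserved factors only so far as they are related to the included covariates, and to an extent that depends on what drives treatment choice.

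**What to change.** In section 6.1.1, delete the switching sentence and name one primary estimator in advance for all contrasts. Either choice removes the dependence on results, and it is the sponsor's to make. PS costs precision: at efficiency 4.0 its standard error is sqrt(4) = 2 times that of the SMLE. The SMLE relies on the outcome model, and section 6.1 notes that its Cox version is one users must implement.

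Report the other estimator as a sensitivity analysis. State that PS is run in the stage-two sample, list its covariates, and show a conventional fit on the same women beside it, so that a difference reflects method and not data.

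In sections 6.1.1 and 6.2, say that PS balances measured covariates, and correlated unmeasured ones only in part. Drop the 90% claim and leave unmeasured confounding to the IVA of section 6.1.2.

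The cost is wording plus one extra fit per contrast; no new data are needed.
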